4.5.2.1. Adverse Events of Special Interest

There are no adverse events of special interest identified for this study.

4.5.2.2. COVID-19 Assessment and COVID-19 AEs

COVID-19 assessments for participants with COVID-19 AEs will be summarized.

4.5.2.3. Impact of COVID-19 Pandemic on Safety Results

The impact of the COVID-19 pandemic on the safety results will be assessed, if any.

Adverse Events

A listing of COVID-19 related AEs (SMQ related to COVID to flag all preferred terms related to COVID-19) will be produced.

If >= 10 participants (groups 1 and 2 combined) have confirmed COVID-19, the following tables will be created:

- 1. Adverse Events by System Organ Class and Preferred Term and Maximum Intensity (AEs before the onset of COVID-19 vs. AEs on and after the onset of COVID-19; Safety Analysis Set)
- 2. Adverse Events by System Organ Class and Preferred Term and Maximum Intensity (AEs on and after the onset of COVID-19; COVID-19 Analysis Set)
- 3. Serious adverse events by system organ class and preferred term and maximum intensity (SAEs before the onset of COVID-19 vs. SAEs on and after the onset of COVID-19; Safety Analysis Set)
- 4. Serious adverse events by system organ class and preferred term and maximum intensity (SAEs on and after the onset of COVID-19; COVID-19 Analysis Set)

4.5.3. Additional Safety Assessments

4.5.3.1. Laboratory Data

Separate summary tables for haematology, and chemistry laboratory tests as well as urine concentration parameters will be produced. Liver function laboratory tests will be included with chemistry lab tests.

Change from baseline in laboratory parameters will be presented for continuous variables, with a summary of baseline values included in the tables. Shift tables of worst-case results post-baseline relative to baseline will be provided for the following tests:

- For lab tests with associated Potential Clinical Importance (PCI) criteria (see Section 6.2.1)
- For categorical urinalysis parameters

Only post-baseline data will be included in these tables. If a participant moves to both a low and a high clinical concern range during the treatment period, then the participant is counted in both categories.

Summaries of hepatobiliary laboratory events including possible Hy's law cases will be provided in addition to what has been described above. Possible Hy's law cases are defined as any elevated alanine aminotransferase (ALT) \geq 3 × upper limit of normal (ULN) and total bilirubin \geq 2 × ULN (>35% direct bilirubin) or ALT \geq 3 × ULN and international normalized ratio (INR) >1.5. Total bilirubin \geq 2×ULN can be within 28 days following the ALT elevation and if direct bilirubin is available on the same day, it must be \geq 35% of total bilirubin. The summary will be produced for worst-case post-baseline only.

4.5.3.2. Vital Signs

A summary table of change from baseline in vital signs will be produced, including systolic blood pressure (SBP), diastolic blood pressure (DBP), heart rate, and temperature.

Shift tables of worst-case results relative to PCI criteria post-baseline relative to baseline will be provided for SBP, DBP and heart rate (see Section 6.2.1).

4.5.3.3. ECG

For all ECG analyses, baseline is taken to be the mean of the triplicate values collected pre-dose Day 1. The following summaries will be provided:

- 1. Summary of Maximum QTc Values Post-Baseline Relative to Baseline by Category
- 2. Summary of Maximum Increase in QTc Values Post-Baseline Relative to Baseline by Category
- 3. Summary of ECG findings (the clinical significance and interpretation of each planned ECG). In the case of triplicate ECG measurements, results will be presented separately by measurement number.
- 4. Summary of change from baseline in ECG values. In the case of triplicate ECG measurements, summaries will use the average of the triplicate.

The QTc data analysis will use the values based on Fridericia formula. For analysis purposes, if QTcF is not available, it will be derived from QTcB.

Shift tables will be provided for QTcF and will be used to detect any clinically important changes:

- Maximum QTc values post-baseline relative to baseline by category defined as
 - o To ≤450msec or No Change
 - o Any increase > 450 msec

- \circ Increase to >450 to <=480
- \circ Increase to >480 to <=500
- o Increase to >500 msec
- Maximum increase in QTc values post-baseline relative to baseline by category defined as:
 - Increase of \leq 30 msec
 - o Increase between 31 and 60 msec
 - o Increase > 60 msec

4.6. Other Analyses

4.6.1. Subgroup analyses

There are no planned subgroup analyses for any of the endpoints.

4.7. Interim Analyses

The details of the planned analysis and timing will be documented in the Interim Analysis Charter.

The decision criteria will be based on predictive probabilities of achieving two decision criteria (at the end of the study) defined in the interim charter, based on the interim data. The prediction of the future data will be based on the posterior distribution of the parameters at interim. The latter will be estimated using the same statistical analysis as described in Section 4.2.2.

4.8. Changes to Protocol Defined Analyses

There is no change or deviation to the originally planned statistical analysis specified in protocol amendment #1 (Dated: 25-FEB-2022).

5. SAMPLE SIZE DETERMINATION

Approximately 64 patients may need to be screened to obtain 48 randomized participants (approximately 30 and 18 participants in Groups 1 and 2, respectively). Participants who have withdrawn from the study, may be replaced at the discretion of the sponsor.

The sample sizes for Groups 1 and 2 are selected to support preliminary assessment of the clinical effect, based on PCFB in the EASI for Groups 1 and 2.

Operating characteristics of some criteria of interest for the both groups of the study have been calculated and presented below.

Group 1:

Based on 30 participants (20 administered GSK1070806 and 10 administered placebo), the probability of different criteria of interest are given in the table below.

A Bayesian linear regression was used, assuming that the PCFB in the EASI follows a Normal distribution. The priors were as follows:

- Placebo arm: a robust meta-analytic predictive (MAP) prior was constructed based on placebo PCFB in the EASI reported in recent clinical trials in AtD. The resulting mixture prior has 28.5% weight on a Normal (-31.56, SD=5.67), 21.5% weight on a Normal (-31.21, SD=11.00) and 50% weight on a Normal (-30, SD = 50), with an effective sample size of 14 participants (expected local-information-ratio (ELIR) method (Neuenschwander, 2020)) assuming a between-participant SD = 50.
- GSK1070806 arm: a vague Normal prior was used, with mean = -30 and SD = 50, corresponding to an effective sample size (ELIR method) of 1 participant assuming a between-participant SD = 50.

Operating characteristics are provided below. A true PCFB in the EASI of -30% in the placebo arm was assumed, based on recent clinical trials in AtD. Various true PCFBs in the EASI for the GSK1070806 arm at Week 12 were assumed, giving various true treatment differences. A between-participant SD of 50% was assumed for both GSK1070806 and Placebo arms.

Criteria	True treatment difference			
	-40%	-25%	-15%	0%
Observing a >75% posterior probability that the true difference from placebo is <-15%	82.6%	43.9%	18.4%	2.5%
Observing a >75% posterior probability that the true difference from placebo is <-7.5%	92.8%	66.6%	37.7%	7.8%
Observing a >97.5% posterior probability that the true difference from placebo is < 0%	68.8%	30.3%	10.9%	1.0%

Group 2:

There are no planned statistical analyses comparing GSK1070806 *versus* placebo. The analysis will be conducted on PCFB in the EASI in the GSK1070806 arm.

Based on 15 participants on GSK1070806, the operating characteristics are given below.

A vague Normal prior was used, with mean = 0 and SD = 1×10^6 , corresponding to an effective sample size (ELIR method) of 0 participant assuming a between-participant SD=50.

Criteria	True PCFB in the EASI in GSK1070806			
	-70%	-55%	-45%	-30%
Observing a >50% posterior probability that the true PCFB in EASI is <-45%	97.4%	78.1%	50.0%	12.3%
Observing a >50% posterior probability that the true PCFB in EASI is <-37.5%	99.4%	91.2%	71.9%	28.1%
Observing a >50% posterior probability that the true PCFB in EASI is <-30%	99.9%	97.4%	87.7%	50.0%

6. SUPPORTING DOCUMENTATION

6.1. Appendix 1 Study Population Analyses

Unless otherwise specified, the study population analyses will be based on the Randomised or Enrolled Analysis Set. A summary of the number of participants in each of the participant level analysis set will be provided.

Study population analyses including analyses of participant's disposition, protocol deviations, demographic and baseline characteristics, prior and concomitant medications will be based on GSK Core Data Standards. Details of planned displays are presented in OPS.

6.1.1. Participant Disposition

A summary of the number and percentage of participants who completed the study as well as those who prematurely withdrew from the study will be provided. Reasons for study withdrawal will be summarized. A participant is considered to have completed the study if they have completed all planned study assessments including the follow-up visit.

Rescreening of screen failures is allowed as per protocol. Rescreened participants will be summarized under their latest participant number.

6.1.2. Demographic and Baseline Characteristics

The demographic characteristics including age, gender, race, ethnicity, height, weight, and BMI will be summarized.

A summary of atopic dermatitis history and characteristics will be provided. The summary will include baseline EASI score (continuous), baseline IGA score (categorical), and duration since diagnosis.

Past medical conditions and current medical conditions as of screening will be summarized separately.

6.1.3. Protocol Deviations

Important protocol deviations (including deviations related to study inclusion/exclusion criteria, conduct of the trial, patient management or patient assessment, prohibited medication) will be summarized.

Protocol deviations will be tracked by the study team throughout the conduct of the study. These protocol deviations will be reviewed to identify those considered as important as follows:

- Data will be reviewed prior to unblinding and freezing the database to ensure all important deviations (where possible without knowing the study intervention details) are captured and categorised in the protocol deviations dataset.
- This dataset will be the basis for the summaries of important protocol deviations.

6.1.4. Prior and Concomitant Medications

Concomitant medications will be coded using both the GSK Drug and WHO Drug dictionaries. However, the summary will be based on GSK Drug dictionary only.

The summary of concomitant medications will be provided by Anatomical Therapeutic Chemical (ATC) classification Level 1 and ingredient, i.e. multi-ingredient medications will be summarized for each individual ingredient rather than a combination of ingredients.

Pre-intervention, Treatment, and Follow up concomitant medications are defined in OPS.

A summary of prohibited medications and Rescue Therapy will be produced by ingredient.

The incidence of use of prohibited medications and Rescue Therapy will be summarised, overall and by topical and non-topical groups. Cumulative proportion of participants receiving prohibited medications / Rescue Therapy during the treatment period will be plotted.

6.1.5. Study Intervention Compliance

Not applicable for this study.

6.1.6. Additional Analyses Due to the COVID-19 Pandemic

A participant is defined as having a suspected, probable or confirmed COVID-19 infection during the study if the answer is "Confirmed", "Probable" or "Suspected" to the case diagnosis question from the COVID-19 coronavirus infection assessment eCRF.

Summary of COVID-19 Assessments for Subjects with COVID-19 Adverse Events and a Listing of Visits impacted by COVID-19 Pandemic will be provided.

6.2. Appendix 2 Data Derivations Rule

6.2.1. Criteria for Potential Clinical Importance

6.2.1.1. Laboratory Values

Haematology					
Laboratory Parameter	Units	Category	Potential Clinical Importance		
			Low Flag (< x)	High Flag (>x)	
		Male	<0.1	>0.54	
Hematocrit	Ratio of	Female	<0.1	>0.54	
Hematocht	1	Δ from BL	>0.075 change from baseline		
	g/L	Male	<100	>185	
Haemoglobin		Female	<100	>165	
Tidemoglobiii		Δ from BL	>25 change from baseline		
Lymphocytes	x10 ⁹ / L		0.8		
Neutrophil Count	x10 ⁹ / L		1.5		
Platelet Count	x10 ⁹ / L		<100	>999	
While Blood Cell Count (WBC)	x10 ⁹ / L		<2		

Clinical Chemistry		
Laboratory Parameter	Units	Potential Clinical Importance
		Low Flag (< x) High Flag (>x)
Albumin	g/L	<30
Corrected Calcium	µmol/L	
-Ages 18-59 years		<1.5 >3.25
-Ages 60-90 years		<1.5 >3.25
Creatinine	µmol/L	
-Male ≥18 yrs	μmol/L	Change from baseline >44.2
-Female ≥18 yrs	µmol/L	Change from baseline >44.2

Clinical Chemistry					
Laboratory Parameter	Units	Potential Clinica	Potential Clinical Importance		
		Low Flag (< x)	High Flag (>x)		
Potassium	mmol/L	<3.0	>6.5		
Sodium	mmol/L	<130	>160		
Blood Urea Nitrogen (BUN)	mg/dl		>40		

Liver Function			
Laboratory Parameter	Units	Category	Potential Clinical Importance
ALT/SGPT	U/L	High	≥ 3x ULN
AST/SGOT	U/L	High	≥ 3x ULN
Alkaline Phosphatase	U/L	High	≥ 2x ULN
Total Bilirubin	µmol/L	High	≥ 2x ULN
Direct Bilirubin			>35%

Urinalysis

A participant is considered to have urinalysis results of PCI, if there is an increase in Protein or an increase in Occult Blood results during the study, or if microscopy is performed.

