NOTE: In cases where the QuantiFERON test is *indeterminate*, the participant may have the test repeated once, but they will not be eligible for the study unless the second test is negative. In cases where the QuantiFERON test is positive, the participant should be followed up as per standard of care.

- 8. **Drug Allergy or hypersensitivity:** history of clinically significant multiple or severe drug allergies or severe post-treatment hypersensitivity reactions (including, but not limited to, erythema multiforme major, linear immunoglobulin A (IgA) dermatosis, toxic epidermal necrolysis, and exfoliative dermatitis).
- 9. **Sensitivity** to any of the study interventions, or components/excipients thereof, in the opinion of the Principal Investigator (or following consultation with the GSK Medical Monitor), contraindicates participation in the study.
- 10. **Hepatic**: current or chronic history of liver disease, or known hepatic or biliary abnormalities (with the exception of Gilbert's syndrome or asymptomatic gallstones).
 - a. Alanine transaminase (ALT) >2x upper limit of normal (ULN).
 - b. Bilirubin >1.5xULN (isolated bilirubin >1.5xULN is acceptable if bilirubin is fractionated and direct bilirubin <35%).
- 11. Cardiology assessment/co-morbidity defined as: corrected Q (QTc) >450 msec (480 msec for those with Bundle Branch Block). Either QTcb (Bazett) or QTcf (Fridericia), machine or manual overread, may be used. The QT correction formula used to determine exclusion and discontinuation should be the same throughout the trial. The QTc should be based on a single value (derived from the average of triplicate readings) of ECG obtained over a brief recording period.
- 12. A participant with either a **clinical abnormality or a laboratory parameter(s)** outside of the reference range (or both) that is not specifically listed in the inclusion or exclusion criteria may only be included if the Investigator, in consultation with the GSK Medical Monitor, agrees and documents that the finding is unlikely to introduce additional risk factors that will not interfere with the study procedures or interpretation.

PRIOR / CONCOMITANT THERAPY

Any patients that are receiving medication(s) detailed in this Section will *not* be eligible for randomisation into the trial.

13. **Surgery:** major surgery (as per investigator's judgement) within 3 months prior to dosing on Day 1.

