10.2. Appendix 2: Clinical Laboratory Tests

The tests detailed in Table 1 will be performed by the central laboratory.

Local laboratory results are only required in the event that the central laboratory results are not available in time for either study intervention administration and/or response evaluation. If a local sample is required, it is important that the sample for central analysis is obtained at the same time. Additionally, if the local laboratory results are used to make either a study intervention decision or response evaluation, the results must be recorded.

Protocol-specific requirements for inclusion or exclusion of participants are detailed in Section 5 of the protocol.

Additional tests may be performed at any time during the study as determined necessary by the investigator or required by local regulations.

Table 1 Protocol-Required Safety Laboratory Tests

| Laboratory Assessments | Parameters | | | | | |
|------------------------------------|--|---------------------------|---|--|---|----------------------------|
| Hematology | Platelet Count Red Blood Cell (R Count Hemoglobin Hematocrit | BC) | RBC Indices: Mean Corpuscular Volume (MCV) Mean Corpuscular Hemoglobin (MCH) %Reticulocytes Absolute reticulocyte count | | White Blood Cell (WBC) count with Differential: Neutrophils Lymphocytes Monocytes Eosinophils Basophils | |
| Clinical Chemistry ¹ | Blood Urea Nitrogen (BUN) | Potassium | | Aspartate Aminotransferase (AST)/ Serum Glutamic- Oxaloacetic Transaminase (SGOT) | | Total and direct bilirubin |
| | Creatinine | Sodium Corrected calcium | | Alanine Aminotransferase (ALT)/ Serum Glutamic-Pyruvic Transaminase (SGPT) Alkaline phosphatase ² | | Total Protein and albumin. |

| Laboratory Assessments | Parameters |
|---------------------------|--|
| Routine Urinalysis | Specific gravity pH, glucose, protein, blood, ketones, bilirubin, nitrite, leukocyte esterase, by dipstick Microscopic examination (if blood or protein is abnormal) |
| Pregnancy testing | Highly sensitive serum or urine human chorionic gonadotropin (hCG) pregnancy test (as needed for women of childbearing potential)3 |
| Other Screening | Follicle stimulating hormone (FSH) and estradiol (as needed in women of non-childbearing potential only) |
| Tests | Alcohol and urine drug screen (to include at minimum: amphetamines, barbiturates, cocaine, opiates, cannabinoids and benzodiazepines)] |

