10.5. Appendix 5: Genetics

USE/ANALYSIS OF DNA

- Genetic variation may impact a participant's response to study intervention, susceptibility, severity and progression of disease. Variable response to study intervention may be due to genetic determinants that impact drug absorption, distribution, metabolism, and excretion; mechanism of action of the drug; disease etiology; and/or molecular subtype of the disease being treated. Therefore, where local regulations and IRB/IEC allow, a blood sample will be collected for DNA analysis
- DNA samples will be used for research related to GSK1070806 or atopic dermatitis and related diseases. They may also be used to develop tests/assays including diagnostic tests) related to GSK1070806 and/or atopic dermatitis. Genetic research may consist of the analysis of one or more candidate genes or the analysis of genetic markers throughout the genome (as appropriate).
- Additional analyses of DNA samples may be conducted if it is hypothesized that this may help further understand the clinical data.
- The samples may be analyzed as part of a multi-study assessment of genetic factors involved in the response to GSK1070806 or study interventions of this class. The results of genetic analyses may be reported in the clinical study report or in a separate study summary.
- The sponsor will store the DNA samples in a secure storage space with adequate measures to protect confidentiality.
- The samples will be retained while research on GSK1070806 (or study interventions of this class) or atopic dermatitis continues but no longer than 15 years after the last participant last visit or other period as per local requirements.

10.6. Appendix 6: Liver Safety: Required Actions and Follow-up Assessments.

Liver chemistry stopping and increased monitoring criteria have been designed to assure participant safety and evaluate liver event etiology.

Liver chemistry stopping criteria and required follow-up assessments

| Liver Chemistry Stopping Criteria | | | |
|---|---|-----------------------|---|
| ALT-absolute | ALT ≥5xULN | | |
| ALT Increase | ALT ≥3xULN persists for ≥4 weeks | | |
| Bilirubin1, 2 | ALT ≥3xULN and bilirubin ≥2xULN (>35% direct bilirubin) | | |
| INR2 | ALT ≥3xULN and INR>1.5 | | |
| Cannot Monitor | ALT ≥3xULN and cannot be monitored weekly for 4 weeks | | |
| Symptomatic3 | ALT ≥3xULN associated with symptoms (new or worsening) believed to be related to liver injury or hypersensitivity | | |

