| Required Actions and Follow-up Assessments | | | |
| Actions Follow-up Assessments | | Follow-up Assessments | |
| Immediately | discontinue study intervention | • | Viral hepatitis serology4 |
| Complete the an SAE data | rent to GSK within 24 hours liver event CRF and complete collection tool if the event also teria for an SAE2 | • | Obtain INR and recheck with each liver chemistry assessment until the transaminases values show downward trend |
| Perform liver chemistry event follow-up assessments Monitor the participant until liver chemistries resolve, stabilize, or return to within Baseline | | • | Obtain blood sample for pharmacokinetic (PK) analysis, with timing to be guided by clinical pharmacokinetics representative on a case by case basis, after last dose5 |
| (see MONITORING below) Do not restart/rechallenge participant with | | • | Serum creatine phosphokinase (CPK) and lactate dehydrogenase (LDH). |
| study intervention unless allowed per protocol and GSK Medical Governance approval is granted (see below). | | • | Fractionate bilirubin, if total bilirubin ≥2xULN |
| If restart/rechallenge not allowed per protocol or not granted, permanently | | • | Obtain complete blood count with differential to assess eosinophilia |
| discontinue study intervention and continue participant in the study for any protocol specified follow-up assessments | | • | Record the appearance or worsening of clinical symptoms of liver injury, or hypersensitivity, on the AE report form |
| MONITORING: For bilirubin or INR criteria: | | • | Record use of concomitant medications on the concomitant medications report form including acetaminophen, herbal |

Liver Chemistry Stopping Criteria

- Repeat liver chemistries (include ALT, AST, alkaline phosphatase, bilirubin and INR) and perform liver event follow-up assessments within 24 hours
- Monitor participant twice weekly until liver chemistries resolve, stabilize or return to within Baseline
- A specialist or hepatology consultation is recommended

For All other criteria:

- Repeat liver chemistries (include ALT, AST, alkaline phosphatase, bilirubin and INR) and perform liver event follow-up assessments within 24-72 hours
- Monitor participant weekly until liver chemistries resolve, stabilize or return to within Baseline

- remedies, other over the counter medications.
- Record alcohol use on the liver event alcohol intake case report form (CRF) page

For bilirubin or INR criteria:

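### Two limits in the SAP's laboratory table misclassify if applied as written: direct bilirubin above 35% has no total-bilirubin condition, and the hematocrit low limit is about a third of the value the table's other limits imply

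*SAP*

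**What the plan says.** Protocol Section 3 makes the incidence of clinically important laboratory findings a secondary safety endpoint, and its footnote leaves the definition to the SAP. SAP 6.2.1.1 supplies the limits. SAP 4.5.3.1 then plans worst-case post-baseline shift tables "For lab tests with associated Potential Clinical Importance (PCI) criteria (see Section 6.2.1").

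**Direct bilirubin.** The liver function part of the table has a row "Direct Bilirubin >35" per cent. Its unit and category cells are blank. The row above it is separate and complete: "Total Bilirubin µmol/L High ≥ 2x ULN". Protocol Appendix 2 puts "Total and direct bilirubin" on the routine chemistry panel, and the Schedule of Activities draws that panel at Days 8, 15, 29, 57, 85, 113 and 169.

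Elsewhere the same fraction appears only as a qualifier of a raised total:
- Protocol 5.2, exclusion 10b: "isolated bilirubin >1.5xULN is acceptable if bilirubin is fractionated and direct bilirubin <35" per cent.
- Protocol 10.6 (Appendix 6): "ALT ≥3xULN and bilirubin ≥2xULN (>35% direct bilirubin"). Its follow-up column adds "Fractionate bilirubin, if total bilirubin ≥2xULN".
- Protocol Appendix 2 (note 1), the SAE definition in 10.3.2 and the Hy's law rule in SAP 4.5.3.1 all pair it with ALT of at least 3xULN and total bilirubin of at least 2xULN.

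**Hematocrit.** The absolute limits are "Male <0.1 >0.54", and the same two values are given for women. Haemoglobin in the next row has a low limit of 100 g/L for both sexes and high limits of 185 (men) and 165 g/L (women). The change-from-baseline limits are 0.075 for hematocrit and 25 g/L for haemoglobin.

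**The concern.** A programmer who follows the table literally computes the direct fraction on every chemistry sample and flags any value above 35%. A fraction of a small total can pass 35% with both values low, so a participant with an unremarkable total bilirubin can be reported as having an important liver finding. The shift table takes the worst of up to 7 scheduled post-dose results, which gives several chances per participant. With 35 participants planned on GSK1070806 and 13 on placebo across the two groups, a few such entries would be visible in the liver display.

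The hematocrit limit errs in the other direction. It looks like a safeguard against low values, but it sits far below the level at which the haemoglobin row beside it already flags.

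**Working it through.** **1. Direct bilirubin, arithmetic on the row as written.** The rule is direct / total > 0.35.
- Total 5, direct 2 µmol/L: 2/5 = 40%, flagged.
- Total 45, direct 10 µmol/L: 10/45 = 22%, not flagged on this row.
- Total 6 µmol/L: flagged once direct exceeds 0.35 × 6 = 2.1 µmol/L. Total 10 µmol/L: once direct exceeds 3.5 µmol/L.

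The documents give no ULN. For an assumed ULN of 17 to 24 µmol/L, a total of 6 is 6/24 = 0.25 to 6/17 = 0.35 of the limit, so well within normal.

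**2. The same row with the raised-total condition of SAP 4.5.3.1 and Appendix 6** (total at least 2xULN):

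| Assumed ULN (µmol/L) | Total must reach | Direct must exceed (0.35 × total) |
|---|---|---|
| 17 | 34 | 11.9 |
| 21 | 42 | 14.7 |
| 24 | 48 | 16.8 |

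**3. How often would normal participants be flagged?** The documents contain no distribution of the direct fraction, so this can only be illustrated. Assume total bilirubin with median 8 µmol/L (log-SD 0.4 between and 0.2 within participants), direct fraction with SD 0.04 to 0.06 between and 0.03 within participants, 7 visits and no drug effect. Share of participants flagged at least once:

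| Assumed mean direct fraction | Unrounded values | Values rounded to whole µmol/L |
|---|---|---|
| 0.20 | 0.7 to 4.2% | 4 to 9% |
| 0.25 | 8.9 to 17.2% | 21 to 28% |
| 0.30 | 41 to 44% | 56 to 59% |

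These figures ignore baseline, whereas the shift tables are relative to baseline. Excluding participants already above 35% on one baseline sample lowers 17.2% to about 11%, and 44% to about 22% (unrounded, between-participant SD 0.06). A range from under 1% to over half, set by assumed inputs, is not an estimate.

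**4. Hematocrit, from the table's own pairs.** Ratio = haemoglobin limit / hematocrit limit; matching hematocrit = 100 / ratio; haemoglobin at hematocrit 0.1 = 0.1 × ratio.

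| Pair | Ratio (g/L) | Hematocrit matching 100 g/L | Haemoglobin at hematocrit 0.1 (g/L) |
|---|---|---|---|
| High, men: 185/0.54 | 342.6 | 0.292 | 34.3 |
| High, women: 165/0.54 | 305.6 | 0.327 | 30.6 |
| Change: 25/0.075 | 333.3 | 0.300 | 33.3 |
| Low, both sexes: 100/0.1 | 1000 | 0.1 | 100 |

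Three pairs agree to within about 12% (342.6/305.6 = 1.12). The low pair is about three times the others. The stated 0.1 is 0.1/0.327 = 31% to 0.1/0.292 = 34% of the matching value.

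**5. What still covers low values.** The haemoglobin limit of 100 g/L and both change limits remain in force. The hematocrit change flag alone misses a fall to 0.30 from a baseline of 0.375 or lower, since 0.375 − 0.30 = 0.075 is not above the limit. At the ratios above, however, hematocrit 0.30 corresponds to a haemoglobin of about 92 to 103 g/L (0.30 × 305.6 to 0.30 × 342.6), where the haemoglobin low flag takes over.

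**The case against.** The best defence is that the direct-bilirubin row was never meant to stand alone. It is the only liver row without a unit or category, it lies directly under total bilirubin, and every other use of 35% is conditional. The table was also read from PDF and may have lost merged cells. This makes a qualifier the likely intention. It does not settle the matter, because nowhere does the SAP text state the condition, and SAP 4.5.3.1 sends every test with a limit in this table to a shift table.

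For hematocrit, nothing in the SAP requires the two low limits to correspond, and haemoglobin does the work anyway. That limits the harm. It does not explain why one pair departs threefold from the other three.

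A reader might infer more than the documents support:
- *That the row could hide a real liver signal.* ALT, AST, alkaline phosphatase and total bilirubin have their own limits, and the Hy's law summary carries its own total-bilirubin condition. None of these changes.
- *That the row would swamp the liver table, or that nearly all its flags would be false.* Both depend on assumed distributions and on assuming no drug effect.
- *That the hematocrit low flag can never fire at a level the haemoglobin row treats as important.* It can, below about 31 to 34 g/L; it simply fires too late to add information.
- *That anaemia would go unreported.* The remaining flags cover it, and no participant missed by the table as a whole has been identified.

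**Conclusion.** Both limits misclassify if applied as written, and neither conclusion needs an outside figure. The direct-bilirubin row can count participants whose total bilirubin is normal; the frequency is unknown. The hematocrit low limit is 31 to 34% of the value implied by the table's other pairs, which makes it nearly inert rather than harmful. The bilirubin conclusion rests on a literal reading of the row; if a qualifier was intended, the fault is an unstated condition rather than a wrong rule. The consequence is confined to the descriptive display of one secondary safety endpoint, with no formal testing of safety data. Severity is minor.

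**What to change.** In SAP 6.2.1.1, before unblinding:
- Define the direct-bilirubin row as direct bilirubin as a percentage of total, applied only when total bilirubin on the same sample meets a stated raised-total condition. Reconcile that condition with SAP 4.5.3.1 and Protocol Appendix 6, which both use at least 2xULN; exclusion 10b uses a different multiple for eligibility. Settle the inequality as well, since SAP 4.5.3.1 writes the fraction both as above 35% and as at least 35%. With a 2xULN condition the row becomes a subset of the total-bilirubin row, so whether it still needs its own shift table is the sponsor's preference.
- Reconcile the hematocrit low limit with the haemoglobin low limit, or remove it and rely on haemoglobin and the change criteria. The choice of clinical value is the sponsor's.

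The cost is one line each in the SAP table and the programming specification, with no new data. Timing matters because removing flags after treatment codes are known would look driven by results.
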